8.8.2.12. Adverse Event (AE) Monitoring

The PI or a qualified designee listed on Form FDA 1572 must assess the severity and relationship to study medication for all AEs (see Section 12.2).

All observed or volunteered AEs regardless of treatment group or suspected causal relationship to the investigational product(s) will be recorded on the AE page(s) of the CRF.

Each PI and research team are responsible for identifying adverse events and reporting them.

For all AEs, the Investigator must pursue and obtain information adequate to determine the outcome of the AE and to assess whether it meets the criteria for classification as an SAE (see Section 5) requiring immediate notification to the Sponsor or its designated representative.

For all AEs, sufficient information should be obtained by the Investigator to determine the causality of the AE. The Investigator is required to assess causality and indicate that assessment on the CRF. For AEs with a causal relationship to the investigational product, follow-up by the Investigator is required until the event or its sequelae resolve or stabilize at a level acceptable to the Investigator, and Sponsor concurs with that assessment.

Adverse events (serious and non-serious) including all suspected unexpected serious adverse reactions (SUSARs) should be recorded on the CRF from the date of informed consent until the end of their participation in the study (i.e., the subject has discontinued or completed the follow-up visit).

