#### 14.1. Adverse Events

Adverse events (AEs) will be coded using the Medical Dictionary for Regulatory Activities (MedDRA) central coding dictionary, version 21.0.

Summary tables for AEs will include treatment-emergent adverse events (TEAEs, defined as AEs occurred during or after the first administration of a study drug). AEs occurred before the first administration of a study drug will be listed separately. Aes occurring 7 days after the last dose of study medication will be listed separately.

Unless otherwise stated, AE analyses will be subject-based, each subject will be counted once in frequency tables at the subject, SOC and preferred term levels, and the denominator for percentages will be the number of subjects in the SAS, in the respective treatment arm (i.e. "as treated" assignment of treatment arms).

AEs will be assigned to study phases (DBT or OLE) based on their start date.

If the start date of an AE is incomplete:

a/ If only day is missing, and if in the same month the treatment was started then the start date of AE will be imputed with the day of first treatment. If treatment started earlier and not in that month then the first day of the month will be used for imputation.

b/ If month and day are missing, and the treatment start date was in the same year then the start date of AE will be imputed with the month and day of the first treatment administration. If the treatment start date was in the previous year, then 01 JAN will be used for imputation.

c/ If the entire AE start date is missing then the date will not be imputed, but the AE will be considered treatment-emergent.

If the end date of an AE is missing, the AE will be considered as "ongoing".

If a subject xperiences a TEAE with a missing causality assessment, then relationship will be categorized as "Related". AEs with a missing causality assessment during the screening period relationship will be categorized as "Unrelated".

If a subject experiences a TEAE with a missing severity assessment, then severity for this TEAE will be categorized as "Severe".

In addition to keeping the 5-level categorization of causality of AEs, they will also be dichotomized into two categories: related/not related. "Related" category comprises events which were classified by the investigator as possibly, probably or related to treatment, whereas "Not Related" category comprises the other two levels of the investigator's assessment ("Unlikely to be related" and "Unrelated").

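### SAP 14.1 classifies AEs with an incomplete start date without using the recorded end date, so an event that ended before first dose can count as treatment-emergent

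*SAP*

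**What the plan says.** SAP 14.1 (Adverse Events) gives three rules for incomplete start dates:

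- Rule (a), day missing: "if in the same month the treatment was started then the start date of AE will be imputed with the day of first treatment". Where dosing began in an earlier month, the first of the AE month is used.
- Rule (b), month and day missing, same year as treatment start: "the start date of AE will be imputed with the month and day of the first treatment administration".
- Rule (c): "If the entire AE start date is missing then the date will not be imputed, but the AE will be considered treatment-emergent".

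The same section describes TEAEs as "defined as AEs occurred during or after the first administration of a study drug" and keeps earlier events out of the TEAE tables: "AEs occurred before the first administration of a study drug will be listed separately". Its only sentence on end dates covers the case where the end date is missing, when the event is taken as ongoing. A missing causality is set to Related for a TEAE but to Unrelated for a screening-period AE. A missing severity on a TEAE is set to Severe.

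On collection, Protocol 8.8.2.12 says AEs "should be recorded on the CRF from the date of informed consent until the end of their participation in the study". Protocol 12.1 also counts events in the screening period as AEs. Protocol 12.3, however, starts collection at the first dose.

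**The concern.** Imputing towards first dose is a sensible conservative default when the timing of an event is unknown. It is not sensible when another field on the same record settles the timing. If the end date precedes first dose, the event cannot have begun on treatment, yet the rules place it there. The derived data then hold a start date after the end date, and an event that the SAP means to list separately enters the TEAE tables.

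The proportion of subjects with TEAEs is a named safety endpoint (Protocol 11, SAP 5.2.2). A moved event with missing causality or severity would also enter the related-AE row or the Grade 3 and above row of the overview in SAP 14.1.1.

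**Working it through.** The plan states no figure on this point, so the check is to apply the rules literally to test records and then to ask how far they can reach.

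**Step 1. Apply the rules.** Assumed first dose: 20 Mar 2016.

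| Recorded start | Recorded end | Rule | Start after rule | Class |
|---|---|---|---|---|
| Mar 2016, day missing | 16 Mar 2016 | (a) | 20 Mar 2016 | TEAE |
| 2016 only | 16 Mar 2016 | (b) | 20 Mar 2016 | TEAE |
| Wholly missing | 16 Mar 2016 | (c) | none | TEAE by declaration |
| Feb 2016, day missing | 1 Mar 2016 | none applies | none | not moved |
| 2015 only | 5 Jan 2016 | none applies | none | not moved |

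In the first two rows the start falls 20 − 16 = 4 days after the end. The last two rows show the limit of the problem: when the partial start lies in a month or year before treatment start, rules (a) and (b) give no instruction, and the event is not pushed into the TEAE tables.

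**Step 2. Apply an end-date condition.** Since 16 Mar is before 20 Mar, the first three records become pre-dose events and go to the listing. No start falls after its end.

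**Step 3. When can rules (a) and (b) reach a pre-dose event?** The event must fall in the first-dose month (a) or year (b). Assume that any day from consent to the day before dosing is equally likely, averaged over all first-dose dates in 2016 (366 days). For consent k days before dosing, with k no longer than a month:

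- same-month share = 1 − [(k + 1)/2] × (12/366)
- same-year share = 1 − [(k + 1)/2] × (1/366), which holds for every k used here

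Visit 2 is at Day −7 ± 5, so k runs from 2 to 12. Consent may also be signed at Visit 1, as early as Day −90. For k = 90 the same-month share was counted day by day.

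| k (days) | Same month, rule (a) | Same year, rule (b) |
|---|---|---|
| 2 | 95.1% | 99.6% |
| 7 | 86.9% | 98.9% |
| 12 | 78.7% | 98.2% |
| 90 | 16.4% | 87.6% |

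These are shares of pre-dose days on which a rule could bite. They are not misclassification rates. Misclassification also needs an incomplete start date and an end date before first dose, and the documents give no frequency for either.

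**Step 4. Weight of one subject.** About 15 subjects at 2:1 (SAP 6.1) gives 15 × 2/3 = 10 and 15 × 1/3 = 5. One subject is 1/10 = 10 points on MN-001 or 1/5 = 20 points on placebo.

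**The case against.** The strongest reply is that the triggering records may hardly exist. Protocol 12.3 collects AEs only from first dose, and the Schedule of Events has no AE review before Day 1. This stands as a limit on frequency. It does not remove the gap: Protocol 8.8.2.12 and 12.1 bring screening events in, Protocol 8.8.2.4 makes significant examination changes since consent AEs, and the SAP has a causality rule for screening-period AEs, so its authors expected some.

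A second reply is that the intent to list pre-dose events separately is already written, and that on-site CRF review (Protocol 13.3) would catch odd dates. Both make an undetected error less likely. Neither overrides an explicit imputation rule that a programmer will follow.

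Third, the rules are the same in both arms, lean towards over-counting TEAEs and do not touch efficacy. That is correct, and it keeps the point minor.

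A reader might infer from the high same-month shares that most pre-dose AEs will be misclassified. The documents do not support that. The share falls to about 16% for consent at 90 days, and most of the conditions needed have no stated frequency. A reader might also infer that every pre-dose AE with a missing start day is wrongly handled. Where the end date is missing, or falls on or after first dose, the conservative imputation is reasonable.

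**Conclusion.** The rules are wrong as written for a narrow set of records: an incomplete start date together with an end date before first dose. For these, rules (a) and (b) produce an impossible date and rule (c) declares treatment emergence against the evidence on the CRF, contrary to the SAP's own separate listing. Missing causality or severity would compound the error.

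Few such records are expected, and fewer still if sites followed Protocol 12.3. The 10-point and 20-point effects rest on arms of about 10 and 5, and on the subject not already being counted for that term. Because subjects are counted once, the overall TEAE proportion moves only if the subject has no other TEAE. A reader might infer that this safety endpoint is materially distorted; nothing in the documents shows that. This is a minor correction, worth making because it is cheap and cannot lose a true TEAE when the end date is correct.

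**What to change.** Add to rules (a)–(c) in SAP 14.1:

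> If the AE end date, complete or partial, shows that the event ended before the first dose, the AE is not treatment-emergent and goes to the pre-dose listing; an imputed start date may not be later than the AE end date.

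Keep the present imputation wherever the end date is missing or does not settle the timing, including an end on the first-dose day. Separately, reconcile Protocol 8.8.2.12 with 12.3 on when AE recording begins, and state in the SAP which was followed.

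The cost is one sentence and one programming condition. No new data are needed: Protocol 12.3 already collects the AE outcome date, and SAP 14.1 already refers to an end date.

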8.8.1.2. Double-Blind Treatment Phase (26 weeks)

Subjects will enter the clinic in the morning prior to breakfast. Once the pre-dose fasting labs have been completed, subjects will be given breakfast except on Baseline Day 1.

Baseline Clinic Visit: Day 1

The following assessment will be done:

- Inclusion/Exclusion criteria review
- Vital signs including supine blood pressure, respiratory rate, heart rate, and temperature
- Urine β-hCG (in pre-menopausal females)
- Concomitant medication review
- Adverse event review
- Dispense study drug
- Dispense patient diary
- 12-lead ECG at Hour 1.5 (\pm 30 minutes) post dose

Once the pre-dose assessments have been completed, the subject will be administered the first dose of MN-001 (2 or 3 tablets of MN-001 250 mg) or matching placebo with water.

Clinic Visits: Months 1, 3 and 6* (± 5 days)

The following assessments will be done:

- Physical examination
- Body weight
- Vital signs including supine blood pressure, respiratory rate, heart rate, and temperature
- 12-lead ECG at Hour 1.5 (± 30 min) post dose

- Fasting safety labs chemistry (including CPK, liver enzymes, lipid panel) hematology, and urinalysis labs
- Urine β-hCG (pre-menopausal females)
- Blood Sample for biomarker (Month 6 only)
- Pulmonary function test (Months 3 and 6 only)
- 6MWT (Months 3 and 6 only)**
- Dyspnea score (MMRC)
- ATAQ-IPF (Months 3 and 6 only)
- Adverse event review
- Concomitant medication review
- Patient diary review
- Dispense study drug (Months 3 and 6 only)
- Study drug accountability
 - * Month 6 Clinic Visit is the start day (Day 1) of the Open-Label Extension (OLE) phase. All subjects will take MN-001 750 mg bid or 500 mg tid.
 - ** Two tests should be performed for 6MWT

Telephone Visits Week 1 (\pm 3 days) and Month 4 (\pm 5 days)

Between clinic visits, subjects will be called by a study team member (e.g., study coordinator or nurse) to collect information regarding their health status. The MMRC will be administered (only Month 4) and adverse events and concomitant medications will be documented.

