### **10.2.** Definition of Study Phases

Double Blind Treatment Phase (DBT Phase)

The DBT Phase starts with Visit 3 which is the Day 1 of the DBT phase.

The DBT Phase ends with end of the day of Visit 8 (Month 6) and assessments taken on this visit will be considered as belonging to the DBT phase.

Open Label Extension Phase (OLE Phase)

The OLE Phase starts on the following day of Visit 8 and ends with Visit 14(Month 13).

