### 10.3. Definition of Baseline

Unless otherwise specified, baseline is defined as the measurement closest to the date of the first administration of Investigational Medicinal Product (IMP), and preceding the first dose of IMP (MN-001 or Placebo).

For the DBT Phase, baseline values will be assessed pre-dose at Visit 3 (Day 1) in this study. For pulmonary function test, 6MWT, MMRC, ATAQ-IPF and 12-Lead ECG, the baseline values will be assessed at Visit 2 (Day -7).

For the OLE Phase, unless otherwise specified, baseline values for those subjects who were taking Placebo in the DBT Phase will be defined as measurements closest to the first administration of MN-001 and preceding the first dose of MN-001. Therefore, these baseline values will be the ones assessed pre-dose on Visit 8 (Month 6) of the DBT phase.

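### SAP 14.1 imputes partial AE start dates without regard to the Month 6 crossover, so former-placebo events that begin on MN-001 can be counted under Placebo

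*SAP*

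**What the plan says.** SAP 14.1 sets the phase from one variable: "AEs will be assigned to study phases (DBT or OLE) based on their start date". The same section then completes partial start dates.

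- **Day missing:** the day of first treatment if that falls in the same month. Otherwise: "If treatment started earlier and not in that month then the first day of the month will be used for imputation".
- **Month and day missing, year of first treatment:** "the start date of AE will be imputed with the month and day of the first treatment administration".
- **Month and day missing, later year:** "If the treatment start date was in the previous year, then 01 JAN will be used for imputation".
- **Date wholly missing:** "If the entire AE start date is missing then the date will not be imputed, but the AE will be considered treatment-emergent". No phase is given.

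SAP 10.2 counts everything up to the end of the Visit 8 (Month 6) day as DBT and starts the OLE the next day. SAP 10.1 defines former-placebo subjects as taking placebo in DBT and MN-001 in the OLE. SAP 14 and 14.1.1 report safety by phase and arm, with one count per subject, preferred term and phase.

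On the boundary day itself, Protocol 8.8.1.2 says: "Month 6 Clinic Visit is the start day (Day 1) of the Open-Label Extension (OLE) phase. All subjects will take MN-001". SAP 10.3 says of the former-placebo open-label baseline: "Therefore, these baseline values will be the ones assessed pre-dose on Visit 8 (Month 6) of the DBT phase". Both imply that the first MN-001 dose of these subjects is taken on a day that SAP 10.2 assigns wholly to DBT.

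**The concern.** Setting a partial date to the earliest plausible day is a sensible way to decide whether an event is treatment-emergent. SAP 14.1 uses the same imputed date for a second purpose, choosing the phase, and there an early date is not neutral. None of the anchors refers to Visit 8 or to the first open-label dose.

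In the randomised MN-001 arm the consequence is a wrong phase but the right drug. In former-placebo subjects the drug is wrong too: an event that began on MN-001 is tabulated under Placebo. That overstates the Placebo double-blind incidence and understates events at these subjects' first exposure to MN-001. Safety and tolerability are secondary objectives, and the Placebo group is very small.

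**Working it through.** The plan gives no figure on this point, so there is nothing to reproduce.

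**Inputs**
- DBT lasts 26 weeks, so Visit 8 is taken at day 26 × 7 = 182 after first dose (window ±5 days, Protocol Table 1).
- The OLE runs 26 × 7 = 182 days after Visit 8 (Month 12), or 182 + 28 = 210 days if the follow-up visit (Month 13) is included, as in SAP 10.2.
- Imputation follows SAP 14.1 and the phase boundary follows SAP 10.2.
- Assumptions: first-dose dates spread evenly over four calendar years (1,461 dates); onsets spread evenly over OLE days; 1 January used for any year after that of first dose.

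**Step 1: logic.** Let V be the Visit 8 date.
- Day missing, month of V: imputed to the 1st of that month, which is never after V, so always DBT. A later month gives a date after V, so OLE.
- Year only, year no later than that of V: imputed to first dose or 1 January, neither of which is after V, so always DBT. A later year gives OLE.

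**Step 2: examples (hypothetical dates)**
- First dose 7 Mar 2016, V = 5 Sep 2016, true onset 15 Sep 2016, ten days after V. Recorded as Sep 2016, it is dated 1 Sep. Recorded as 2016, it is dated 7 Mar. Both are DBT.
- First dose 10 Sep 2017, V = 11 Mar 2018, true onset 20 Jun 2018. Recorded as 2018, it is dated 1 Jan 2018, again DBT.

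**Step 3: share of OLE onsets placed in DBT, Visit 8 day excluded.** Denominators are 1,461 × 182 = 265,902 and 1,461 × 210 = 306,810.

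| Missing part | OLE to Month 12 | OLE to Month 13 |
|---|---|---|
| None | 0 | 0 |
| Day | 21,520/265,902 = 8.1% | 21,520/306,810 = 7.0% |
| Month and day | 199,290/265,902 = 74.9% | 218,190/306,810 = 71.1% |

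The day-missing window averages 21,520/1,461 = 14.7 days per subject.

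**Step 4: opposite direction.** For an onset on or after first dose, the imputed date is never later than the true one. DBT onsets placed in OLE: 0.

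**Step 5: Visit 8 day.** If that day is counted as post-dose, a fully dated event on it is also misplaced: 1/183 = 0.5% or 1/211 = 0.5% of OLE onset days. The other shares become:
- Day missing: 22,981/267,363 = 8.6% or 22,981/308,271 = 7.5%.
- Year only: 200,751/267,363 = 75.1% or 219,651/308,271 = 71.3%.

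The 0.5% is an upper bound, because note e to Protocol Table 1 has open-label drug dispensed only after the visit procedures.

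**Step 6: sensitivity.** With Visit 8 at day 177 or 187 and the OLE length held fixed, the shares do not change. With the end of follow-up held fixed instead, they are 6.8–8.3% (day missing) and 70–76% (year only).

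**Step 7: effect on a table.** About 15 subjects at 2:1 gives 15 × 1/3 = 5 on placebo. One subject wrongly counted changes a Placebo incidence by 1/5, or 20 percentage points.

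**The case against.** The strongest counter-argument is that the effect may never arise. Protocol 12.3 asks for the onset date of every event, and events are reviewed at every contact from Day 1, including a call one week after the OLE starts and a visit at Month 7. Events in the rest of the crossover month should therefore be well dated. An event with an unknown month is unlikely when reviews are at most about three months apart. This stands as a limit on practical weight: the shares above are conditional on a partial date occurring.

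A second argument is that the MN-001 arm's OLE events also move back, so both double-blind columns rise. If partial dating and OLE event rates were alike in the two arms, the between-arm difference in events per subject would change little. That is true under those assumptions, but the documents do not support them: one arm is at first exposure and the other is in its second half-year. Nor does it undo the wrong drug attribution or the events lost from the Former Placebo OLE column.

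Two possible rescues fail. Reading first treatment as the first MN-001 dose puts the date at Visit 8, which SAP 10.2 still counts as DBT. Protocol 12.3 has events entered on the CRF page for the study period, but SAP 14.1 does not use that page. Listings would let a careful reader spot a misplaced event; the tables would still be wrong.

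**Conclusion.** The concern holds, as a minor one. The rule as written gives the wrong phase for every OLE event dated only to the crossover month, and for every OLE event dated only to a year no later than the Visit 8 year. For former-placebo subjects it also gives the wrong drug, always from MN-001 to Placebo. The shares rest on evenly spread first-dose and onset dates, which are assumptions. The number of partially dated events cannot be derived from the documents and may be small or zero. The missing phase rule for undated events is a gap in the same section. The Visit 8-day conflict is separate and smaller. The affected tables are descriptive, so the consequence is confined to those counts, though with about five placebo subjects a single event can be visible.

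**What to change.** Reconcile Protocol 8.8.1.2, SAP 10.2 and SAP 10.3 on when the OLE starts for analysis. Keep Visit 8 assessments, and events found at them or present before open-label dispensing, in DBT. Assign an event on the Visit 8 day to OLE only if it is recorded as starting after the first open-label dose; leave the rest in DBT, flagged.

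For partial or missing start dates, apply the same steps in both arms:

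1. An event first reported before the first open-label dose is DBT.
2. An event shown to be new after Visit 8 (absent at the Visit 8 review, or recorded as starting after the open-label dose) is OLE, and imputation may not date it earlier.
3. Any other event whose possible onset spans Visit 8 is listed as ambiguous, and counts by phase are shown under both assignments.

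Simply defaulting ambiguous dates to OLE would reverse the error: about 8% of day-missing and 75% of year-only DBT onsets would move to OLE. Date of report alone is not a safe default either. If every event is reported at the next scheduled review, no onset before Visit 8 is first reported after it. If every event is reported one review late, about 8% of day-missing and 30% (78,883/265,902) of year-only DBT onsets are both ambiguous and first reported after Visit 8. Hence step 3.

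The cost is a few lines in the SAP, some programming and one extra table. This assumes that the CRF captures the visit of first report or the study period; the CRF is not among the documents. If it captures neither, step 3 applies to every partial date that spans Visit 8.

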#### 14.1.1. All Adverse Events

An overview of number of subjects (%) with treatment-emergent AEs will be presented for the main AE categories (All AEs, AEs leading to discontinuation, SAEs, SAEs leading to discontinuation, AEs with at least Grade 3 severity (Severe AEs, Life-threatening AEs, Deaths), AEs and SAEs with relationship to IMP as possibly related, probably related, or related) by treatment arm and phase.

The number (%) of subjects with treatment-emergent AEs will be presented by phase, treatment arm, System Organ Class and Preferred Term (MedDRA), AE severity, and relationship to study drug (for both AEs and SAEs). Each subject will be counted only once within each preferred term per study phase. If a subject experiences more than one AE within a preferred term for the same recording phase, only the AE with the strongest relationship or highest severity, as appropriate, will be included in the summaries by relationship and severity.

